9.2.1.1 Adverse Events of Interest

Because of the characteristics of the disease under study and ozanimod in particular, some AEs are considered adverse event of interest (AEI). AEIs may be serious or nonserious. Such events may require further investigation to better characterize and understand them. In the ozanimod clinical development program, potential AEIs that may be a result of S1P1 modulation will be closely monitored during the study. These AEIs include bradycardia, heart conduction abnormalities (second degree and higher AV block), macular edema, malignancy, serious or opportunistic infection, pulmonary effects, hepatic effects, posterior reversible encephalopathy syndrome, progressive multifocal leukoencephalopathy (PML), and events associated with orthostatic hypotension (eg, dizziness, lightheadedness, syncope, seizure). The Sponsor may request additional medical information concerning AEIs that are nonserious.

- Bradycardia and heart conduction abnormalities (eg, symptomatic bradycardia, 2nd degree AV block, QT prolongation) will be screened for per the SOA ([Section 2](#)). First dose observation or cardiologist opinion will be per the SOA ([Section 2](#)). Investigators should be particularly cautious with participants with pulse rates < 55 beats per minute prior to administration of ozanimod. Atropine IV is recommended as first-line treatment for bradycardia, up to a

maximum daily dose of 3 mg. In general, common guidelines for treatment of bradycardia (eg, advanced cardiac life support) should be followed as appropriate.

- Macular edema
 - For participants with symptoms of new-onset macular edema that develop following initiation of treatment, a general ophthalmologic examination, including eye history, visual acuity, and dilated ophthalmoscopy must be performed.
 - Ozanimod must be discontinued in any participant who has a confirmed diagnosis of new-onset macular edema.
 - Participants with a diagnosis of macular edema must be followed up monthly and more frequently, if needed, based on the ophthalmologist's clinical judgment.
- Malignancy: Participants should be carefully monitored for malignancies (including dermatologic malignancy). The investigator will complete dermatological examinations to monitor the potential development of new cutaneous malignancies during the study. Participants with any suspicious finding noted during the examination will be referred to an appropriately qualified dermatologist for evaluation and treatment, if warranted.
- Serious or opportunistic infection: Tuberculosis, serious bacterial infections, systemic fungal infections, viral infections, such as herpes infections (including herpes zoster and disseminated herpes simplex), and protozoan infections will be considered AEIs.
- Pulmonary effects: If a participant discontinues due to a respiratory AE, the investigator should ensure that the participant has had adequate evaluations, as clinically indicated by a pulmonologist (consider pulmonary function tests, chest X-ray, or high-resolution computed tomography, based on findings of the other examinations), at the time of the AE.
- Hepatic effects: If participants have elevations in liver function tests (LFTs; ALT or/and AST) $\geq 3 \times$ ULN, a retest should be performed as soon as possible but no later than 14 days after the original test. Upon confirmation of the abnormality, retests should be performed weekly until the elevated LFT decreases to below $3 \times$ ULN. At any time, if any of the following occur and there are no apparent alternative causes for the finding, the study intervention must be permanently discontinued:
 - ALT or AST $> 8 \times$ ULN or
 - ALT or AST $> 5 \times$ ULN with confirmation within 2 weeks or
 - ALT or AST $> 3 \times$ ULN and (total bilirubin $> 2 \times$ ULN or INR > 1.5) or
 - ALT or AST $> 3 \times$ ULN with the appearance of fatigue, nausea, vomiting, right upper quadrant pain or tenderness, fever, rash, and/or eosinophilia ($> 5\%$).
- The investigator should establish causality.
- After discontinuation due to elevation of ALT or AST $> 5 \times$ ULN or concurrent elevations of ALT or AST $> 3 \times$ ULN and bilirubin $> 2 \times$ ULN, further liver function evaluations should be performed (for example, coagulation panel and alkaline phosphatase) in consultation with the Medical Monitor.
- Posterior reversible encephalopathy syndrome (PRES) is a syndrome characterized by sudden onset of severe headache, confusion, seizures, and visual loss. If a participant develops any unexpected neurological or psychiatric symptoms/signs (eg, cognitive deficits, behavioral changes, cortical visual disturbances, or any other neurological cortical symptoms/signs), any

symptom/sign suggestive of an increase of intracranial pressure, or accelerated neurological deterioration, the physician should promptly schedule a complete physical and neurological examination and should consider magnetic resonance imaging (MRI). If PRES is suspected, treatment with study intervention should be discontinued.

- PML: In the event of any neurological decline while on ozanimod, the participant should be urgently evaluated by a neurologist.
 - PML is an opportunistic viral infection of the brain caused by the John Cunningham virus that typically occurs in patients who are immunocompromised and may lead to death or severe disability. John Cunningham virus infection resulting in PML has been associated with some risk factors (eg, polytherapy with immunosuppressants, severely immunocompromised patients). PML has been observed in patients treated with immunomodulators, including ozanimod.
 - Typical symptoms associated with PML are diverse, progress over days to weeks, and include progressive weakness on one side of the body or clumsiness of limbs, disturbance of vision, and changes in thinking, memory, and orientation leading to confusion and personality changes.
 - Investigators should be vigilant for clinical symptoms or other findings that may be suggestive of PML. If PML is suspected, a neurologist consultation should be obtained, and an MRI scan should be requested. Treatment with ozanimod should be suspended until PML has been excluded. If confirmed, treatment with ozanimod should be discontinued.

9.2.2 *Method of Detecting AEs and SAEs*

AEs can be spontaneously reported or elicited during open-ended questioning, examination, or evaluation of a participant. Care should be taken not to introduce bias when collecting AEs and/or SAEs. Inquiry about specific AEs should be guided by clinical judgment in the context of known AEs, when appropriate for the program or protocol.

9.2.3 *Follow-up of AEs and SAEs*

- Nonserious AEs should be followed to resolution or stabilization, or reported as SAEs if they become serious (see [APPENDIX 5](#)).
- Follow-up is also required for nonserious AEs that cause interruption or discontinuation of study intervention and for those present at the end of study intervention, as appropriate.
- All identified nonserious AEs must be recorded and described on the nonserious AE page of the eCRF. Completion of supplemental eCRFs may be requested for AEs and/or laboratory abnormalities that are reported/identified during the course of the study.

All SAEs will be followed until resolution, until the condition stabilizes, until the event is otherwise explained, or until the participant is lost to follow-up (as defined in [Section 8.3](#)).

Further information on follow-up procedures is given in [APPENDIX 5](#).

9.2.4 Regulatory Reporting Requirements for SAEs

- Prompt notification of SAEs by the investigator to the Sponsor is essential so that legal obligations and ethical responsibilities toward the safety of participants and the safety of a product under clinical investigation are met.
- An investigator who receives an investigator safety report describing SAEs or other specific safety information (eg, summary or listing of SAEs) from the Sponsor will file it along with the product label and will notify the IRB/IEC, if appropriate according to local requirements.

The Sponsor or designee must report AEs to regulatory authorities and ethics committees according to local applicable laws and regulations. A SUSAR (suspected, unexpected serious adverse reaction) is a subtype of SAE and must be reported to the appropriate regulatory authorities and investigators following local and global guidelines and requirements.

9.2.5 Pregnancy

If, following initiation of the study intervention, it is subsequently discovered that a participant is pregnant or may have been pregnant at the time of study exposure, including for at least intervention after study product administration, the investigator must immediately notify the BMS Medical Monitor/designee of this event. Then, they must complete and forward a Pregnancy Surveillance Form to the BMS designee within 24 hours of awareness of the event and in accordance with SAE reporting procedures described in [APPENDIX 5](#).

Follow-up information regarding the course of the pregnancy, including perinatal and neonatal outcome and, where applicable, offspring information, must be reported on the Pregnancy Surveillance Form. Protocol-required procedures for study discontinuation and follow-up must be performed with the participant.

9.2.6 Laboratory Test Result Abnormalities

The following laboratory test result abnormalities should be captured on the nonserious AE eCRF page or SAE eCRF, as appropriate. Paper forms are only intended as a back-up option when the electronic system is not functioning.

- Reductions in absolute lymphocyte count (ALC) levels for participants in this study are an expected primary PD effect. If $ALC < 200 \text{ cells}/\mu\text{L}$ results are observed during the study, the investigator will be notified and asked to repeat the laboratory tests within 14 days. If the repeat ALC is confirmed below the $200 \text{ cells}/\mu\text{L}$ limit, the investigator will temporarily discontinue study intervention. Laboratory testing will be repeated weekly until the ALC is $> 500 \text{ cells}/\mu\text{L}$. For participants who have a confirmed ALC below the $200 \text{ cells}/\mu\text{L}$ limit and decide to permanently discontinue study intervention, central laboratory testing will continue every 14 days (± 3 days) after the end of treatment visit until it is above the lower limit of normal or until the ALC is considered to have stabilized and/or reached a level that is not clinically significant. Reductions in ALC, in general, need not be reported as AEs unless there are clinical consequences. The decision to report decreased ALC as an AE is at the investigator's discretion.
- Any laboratory test result that is clinically significant or meets the definition of an SAE.

- Any laboratory test result abnormality that required the participant to have study intervention discontinued or interrupted.
- Any laboratory test result abnormality that required the participant to receive specific corrective therapy.

It is expected that, wherever possible, the clinical term would be used by the reporting investigator rather than the laboratory term (eg, anemia vs low Hb value).

9.2.7 Potential DILI

Wherever possible, timely confirmation of initial liver-related laboratory abnormalities should occur prior to the reporting of a potential DILI event. All occurrences of potential DILIs meeting the defined criteria must be reported as SAEs (see [Section 9.2](#) and [APPENDIX 5](#) for reporting details).

A potential DILI is defined as:

- Aminotransferase (AT; ALT or AST) elevation $> 3 \times \text{ULN}$
AND
- Total bilirubin $> 2 \times \text{ULN}$, without initial findings of cholestasis (elevated serum alkaline phosphatase)
AND
- No other immediately apparent possible causes of AT elevation and hyperbilirubinemia, including, but not limited to, viral hepatitis, pre-existing chronic or acute liver disease, or the administration of other drug(s) known to be hepatotoxic.

9.2.8 Other Safety Considerations

Any significant worsening of conditions noted during interim or final physical examinations, 12-lead ECG, X-ray filming, or any other potential safety assessment required or not required by the protocol should also be recorded as a nonserious AE or SAE, as appropriate, and reported accordingly.

9.3 Expedited Reporting of SUSARs

For regulatory reporting, the BMS Drug Safety team is responsible for determining the expectedness of reported events that are suspected to be related to ozanimod based on the product label. Upon assessment and confirmation, SUSARs will be distributed per agreed contractual obligations between BMS and PPD.

- Reporting to global regulatory authorities/agencies will be handled by the BMS Drug Safety team.
- Reporting to Ethics Committees will be handled as follows:
 - For countries where reporting obligations to the IEC/IRB are delegated to PPD, the pharmacovigilance (PVG) team will ensure distribution to the appropriate IEC/IRB.

- For countries where reporting obligations to the IEC/IRB fall under the responsibility of the principal investigators (PIs), the PPD PVG team will distribute the reports to the PIs via PPD's LifeSphere system. The PIs will retrieve the safety reports from LifeSphere and perform onward submission to their corresponding IECs/IRBs per current local regulations.

This also applies for distribution of aggregate reports (eg, 6-monthly SUSAR line listings and Development Safety Update Report), based on the delegation of reporting tasks between PPD and BMS.

9.4 Overdose

An overdose is any dose of IP given to a participant or taken by a participant that exceeds the dose described in the protocol. Any overdose, with or without associated AEs, must be promptly reported to the Medical Monitor or other designated Drug Safety Center. The overdose should be recorded in the study exposure eCRF. AEs associated with an overdose should be reported in relevant AE/SAE sections in the eCRF.

In the event of an overdose, the investigator should:

- Contact the Medical Monitor immediately.
- Closely monitor the participant for AEs/SAEs and laboratory abnormalities, as deemed appropriate by investigator.
- Document the quantity of the excess dose, as well as the duration of the overdosing in the eCRF.

Decisions regarding dose interruptions or modifications will be made by the investigator in consultation with the Medical Monitor based on the clinical evaluation of the participant.

9.5 Safety

Planned time points for all safety assessments are listed in the SOA ([Section 2](#)).

9.5.1 Physical Examinations

Physical examinations will be performed at the time points specified in the SOA (Section 2). Physical examinations will be performed by an investigator-designated medical doctor or advanced practitioner (eg nurse practitioner, physician assistant). Findings must be recorded in the appropriate section of the eCRF.

9.5.2 Vital Signs

Vital signs will be measured at the time points specified in the SOA (Section 2).

9.5.3 12-lead ECG

12-lead ECG will be performed at screening, as specified in the SOA (Section 2). ECG will be read locally. Clinically significant 12-lead ECG findings must be recorded in the appropriate section of the eCRF and should be discussed with the BMS Medical Monitor or designee.

9.5.4 Clinical Safety Laboratory Assessments

- Investigators must document their review of each laboratory safety report.
- Refer to Table 9.5.4-1 for details related to the clinical safety laboratory assessments and to the SOA ([Section 2](#)) for their time points.

A central laboratory will perform the analyses and will provide reference ranges for these tests.

[figure not shown]
Results of the clinical laboratory tests must be available prior to the first dose of study intervention on Day 1.

Table 9.5.4-1: Clinical Safety Laboratory Assessments

CBC and Differential Count	
Hb	
Hematocrit	
Total leukocyte count, including differential	
Platelet count	
Biochemistry	
ALT	Total protein
AST	Albumin
Total bilirubin	Sodium
Direct bilirubin	Potassium
Alkaline phosphatase	Chloride
Lactate dehydrogenase	Calcium
Creatinine	Phosphorus
BUN	Magnesium
Uric acid	
Fasting glucose	
Urinalysis	
Protein	
Glucose	
Blood	
Leukocyte esterase	
Specific gravity	
pH	
Microscopic examination of the sediment if blood, protein, or leukocytes esterase are positive on the dipstick	
Other Analyses	
Pregnancy test (screening only; serum or urine)	
Varicella IgG (screening only)	
[REDACTED]	

Table 9.5.4-1: Clinical Safety Laboratory Assessments

Urine beta-hCG test (WOCBP only)
FSH (optional; screening only [may be used to exclude childbearing potential in peri-menopausal females])
BUN, blood urea nitrogen; CBC, complete blood count; FSH, follicle-stimulating hormone; [REDACTED]
[REDACTED] IgG, immunoglobulin G.

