FSH ^f	X							Optional. See footnotes
TDM Test ^g	X							Optional. See footnotes
Diagnostic Test for SARS-CoV-2	X							Participants must have a negative SARS-CoV-2 PCR test result prior to Day 1, in accordance with site standard practices
Stool Collection								
For Clostridium difficile Testing (and stool infectious screen)	X						x ^h	Stool test results from anytime within 30 days prior to starting first dose of study intervention can be considered for screening process. Results must be documented, if obtained locally.

Table 2-1: Schedule of Activities for Year 1 (IM047029)

Procedure	Screening (Days -28 to -1)	Week 0 (Day 1)	Week 4 (Day 28)	Week 12 (Day 84)	Week 26 (Day 182)	Week 52 (Day 365)	Unscheduled ^a	Notes
Visit Window (± n Days)			7	7	7	14		
For Culture, Ova, and Parasites ⁱ	X							or stool PCR - see footnotes
Endoscopy and Biopsies^j								
Cohort 1 (Advanced Therapy-naïve Cohort)	X			X				Results from endoscopy (colonoscopy or sigmoidoscopy) performed within 60 days prior to first dose of study intervention may be considered for the screening process. Images must be documented to confirm severity. In the setting of historic (prior) endoscopy documentation, biopsy tissue will not be collected.
Cohort 2 (Advanced Therapy-exposed Cohort)	X				X			Results from endoscopy performed within 60 days prior to first dose, may be considered for the screening process. Images must be documented to confirm severity. In the setting of historic (prior) endoscopy documentation, biopsy tissue will not be collected.
Additional Efficacy Assessments^k								
Site Calculates Modified Mayo Score	X			X ^l	X ^m			Required for eligibility assessment

Table 2-1: Schedule of Activities for Year 1 (IM047029)

Procedure	Screening (Days -28 to -1)	Week 0 (Day 1)	Week 4 (Day 28)	Week 12 (Day 84)	Week 26 (Day 182)	Week 52 (Day 365)	Unscheduled ^a	Notes
Visit Window (± n Days)			7	7	7	14		
Baseline (prior to flare) SF	X							
PGA Collection	X	X	X	X	X	X		Physician-reported
RB Subscore	X	X	X	X	X	X		Recorded for 7 days prior to Day 1, daily for the first 12 weeks of the study, and 7 days prior to each study visit thereafter
SF Subscore	X	X	X	X	X	X		
HRQOLⁿ								
IBDQ		X	X	X	X	X		

Table 2-1: Schedule of Activities for Year 1 (IM047029)

Procedure	Screening (Days -28 to -1)	Week 0 (Day 1)	Week 4 (Day 28)	Week 12 (Day 84)	Week 26 (Day 182)	Week 52 (Day 365)	Unscheduled ^a	Notes
Visit Window (± n Days)		7	7	7	14			
Healthcare Resource Utilization^b								

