^e WOCBP only. Pregnancy test anytime within 7 days prior to day of study intervention initiation is permissible – if pregnancy test is done locally, it must be documented.

^f Optional test of FSH level may be used to exclude childbearing potential in peri-menopausal females.

^g For all biologics, the washout period is 8 weeks or 5 elimination half lives, which ever is shorter, but it may be waived with the demonstration of absent drug levels on TDM assay.

ⁱ Stool PCR panel may be performed as an alternative to stool culture if that is in routine clinical use at a site.

^j Endoscopy- and biopsy-related procedure details will be provided to the sites in a separate document/manual.

^k A brief description about additional efficacy assessments is provided in [Section 9.1](#).

^l Only for Cohort 1.

^m Only for Cohort 2.

ⁿ A brief description about HRQOL assessments is provided in [Section 9.1.2.2](#).

^o A brief description about healthcare resource utilization assessments is provided in [Section 9.10](#).

^p Ozanimod titration will occur during the first 7 days of study intervention exposure, per label ([Table 7.1-2](#)). Participants will receive a phone call on Day 5 (when titrating their dose from 0.23 mg to 0.46 mg) and again on Day 8 (when titrating their dose from 0.46 mg to 0.92 mg) as a reminder about the dose adjustment.

Table 2-2: Schedule of Activities for Year 2 (IM047029)

Procedure	Week 104 EOT/ET ^a (Day 728)	Week 116 PTFU (Day 812)	Unscheduled ^b	Notes
Visit Window (± n Days)	14	14		
Concomitant Medications	X	X		Assess for change in concomitant medications (see Section 7.7)
UC Medications	X	X		
Tobacco / e-cigarette vape use	X	X		Assess for change in use
Physical Examination				See Section 9.5.1 for details
Weight	X	X		
Vital Signs (HR, BP, Temperature [°C])	X	X		
Complete Physical Examination	X			
Interim Physical Examination		X		
Electronic Diary (eCOA)				
Site Review of Electronic Daily Diary Compliance	X	X	X	
Blood and Urine Tests^c				See Section 9.5.4 for details
CBC and Differential Count	X		X	
Biochemistry ^d	X		X	

Table 2-2: Schedule of Activities for Year 2 (IM047029)

Procedure	Week 104 EOT/ET ^a (Day 728)	Week 116 PTFU (Day 812)	Unscheduled ^b	Notes
Visit Window (± n Days)	14	14		
Additional Efficacy Assessments^e				
PGA Collection	X	X		Physician-reported
RB Subscore	X	X		
SF Subscore	X	X		Recorded for 7 days prior to each study visit
HRQOL^f				
IBDQ	X	X		
Healthcare Resource Utilization^g				
AE Reporting				

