- a) Documentation of an inadequate response, loss of response, or intolerance to a treatment course of one class of approved biologics (and should not have been treated with additional classes of approved biologics), including:
 - i) Anti-TNF agents (eg, infliximab, adalimumab, golimumab, certolizumab, anti-TNF biosimilars).
 - ii) Anti-integrin inhibitors (eg, vedolizumab).
 - iii) Anti-IL-12p40 biologics (eg, ustekinumab).
 - iv) Anti-IL-23p19 biologics (eg, mirikizumab, risankizumab).
 - v) Other biologics that may become approved for clinical use in this UC study during the course of the study (please discuss with Medical Monitor).
- b) Not Applicable Per Protocol Amendment 01: Patient may have been previously treated with 6-mercaptopurine/AZA, but not concomitantly over the course of the study, and not for at least 30 days prior to the first study intervention administration.

- c) Biologic agents should be discontinued at least 8 weeks prior or at least 5 elimination half lives prior to study intervention initiation, whichever is shorter. Washout period may be waived with the demonstration of absent drug levels on a therapeutic drug monitoring (TDM) assay.
- d) 6-mercaptopurine/AZA or methotrexate:
 - i) Participant may have been previously treated: with 6-mercaptopurine/AZA or methotrexate.
 - ii) Participant may not take these agents concomitantly over the course of the study.
 - iii) These agents must be discontinued prior to day of starting study intervention.

6) Dose Stabilization and Prohibited Concomitant Medications

- a) Compliance with the washout periods for prohibited concomitant medications, as listed in [Table 7.7-1](#).
- b) Must meet the dose stabilization criteria for permitted concomitant medications, as listed in [Table 7.7-3](#).

7) Reproductive Status

- Investigators shall counsel WOCBP participants on the importance of pregnancy prevention and the implications of an unexpected pregnancy.
- The investigator shall evaluate the effectiveness of the contraceptive method in relationship to the first dose of study intervention.
- Local laws and regulations may require the use of alternative and/or additional contraception methods.

a) Female Participants:

- i) Women who are not of childbearing potential are exempt from contraceptive requirements. Evidence to support this status must be included in source documents.

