APPENDIX 4 WOMEN OF CHILDBEARING POTENTIAL DEFINITIONS AND METHODS OF CONTRACEPTION

Appendix 4 provides general information and definitions related to WOCBP and methods of contraception that can be applied to most clinical trials. For information specific to this study regarding acceptable contraception requirements for female participants, refer to [Section 6.1](#) of the protocol. Only the contraception methods described in Section 6.1 are acceptable for this study.

DEFINITIONS

Woman of Childbearing Potential

A woman is considered fertile following menarche and until becoming postmenopausal unless permanently sterile. Permanent sterilization methods include hysterectomy, bilateral salpingectomy, and bilateral oophorectomy.

Women in the following categories are not considered WOCBP:

- Premenarchal
- Pre-menopausal female with one of the following:
 - Documented hysterectomy
 - Documented bilateral salpingectomy
 - Documented bilateral oophorectomy
- Post-menopausal female
 - A post-menopausal state is defined as 12 months of amenorrhea in a woman over the age of 45 years in the absence of other biological or physiological causes. In addition, females under the age of 55 years must have a serum follicle-stimulating hormone (FSH) level > 40 mIU/mL to confirm menopause.

Note: Documentation can come from the site personnel's review of the participant's medical records, medical examination, or medical history interview.

- 1-week minimum for vaginal hormonal products (rings, creams, gels)
- 4-week minimum for transdermal products
- 8-week minimum for oral products

Other parenteral products may require washout periods as long as 6 months. If the serum FSH level is > 40 mIU/mL at any time during the washout period, the woman can be considered postmenopausal.

End of Relevant Systemic Exposure

End of relevant systemic exposure is the time point at which the study intervention (IMP and other study interventions, ie, non-IMP/auxiliary medicinal product required for study) or any active major metabolites have decreased to a concentration that is no longer considered relevant for human teratogenicity or fetotoxicity. This should be evaluated in the context of safety margins from the no-observed-adverse-effect level or the time required for 5 half-lives of the study intervention to pass.

METHODS OF CONTRACEPTION

Local laws and regulations may require use of alternative and/or additional contraception methods.

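### Two FSH table entries let the test rule out childbearing potential in peri-menopausal women, a group that Appendix 4 does not exempt

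*Combined protocol and SAP*

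**What the plan says.** Three places in the protocol bear on how FSH sets childbearing status.

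- **Section 9.5.4, Table 9.5.4-1** lists "FSH (optional; screening only [may be used to exclude childbearing potential in peri-menopausal females" under other analyses.
- **Section 2, Table 2-1** marks the FSH row "Optional. See footnotes", and footnote f reads "Optional test of FSH level may be used to exclude childbearing potential in peri-menopausal females".
- **Appendix 4** sets the default: "A woman is considered fertile following menarche and until becoming postmenopausal unless permanently sterile". It then says "A post-menopausal state is defined as 12 months of amenorrhea in a woman over the age of 45 years", with no other biological or physiological cause, and adds: "In addition, females under the age of 55 years must have a serum follicle-stimulating hormone (FSH) level > 40 mIU/mL to confirm menopause". Its non-WOCBP categories are premenarchal, surgically sterile and post-menopausal. Peri-menopausal is not among them. A separate sentence, after a list of washout intervals for hormonal products, allows a woman to be considered postmenopausal if FSH exceeds 40 mIU/mL at any time in the washout. It does not repeat the amenorrhea condition.

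Section 6.1 uses the term WOCBP without defining it. Criterion 7a(i) states the consequence: "Women who are not of childbearing potential are exempt from contraceptive requirements". Table 2-1 footnote e restricts the pregnancy test to WOCBP.

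**The concern.** The two table entries attach a purpose to the FSH test, excluding childbearing potential, and name a population for it, peri-menopausal women. Appendix 4 gives that population no route out of childbearing status unless the woman meets the post-menopausal definition or the washout sentence applies. Staff who classify a woman from the schedule or laboratory table, and staff who classify her from the appendix, can reach different answers on the same facts.

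The status has direct consequences. It decides whether she needs contraception during treatment and for 90 days afterwards (Sections 6.1 and 6.3), and whether she is pregnancy-tested at all. Fetal risk is a named risk of the study drug in Table 3.3.1-1. Table 2-1 schedules pregnancy tests at screening and Day 1 only, and Table 2-2 schedules none, so no later planned test would reveal a misclassification. For a participant who completes treatment, the exemption runs from Day 1 through Week 104 (Day 728) and the 90 days after: 728 + 90 = 818 days.

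**Working it through.** The plan gives no figure to reproduce on this point. The check is to set the passages side by side and classify the possible cases.

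**Conditions stated in each place**

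| | Table 9.5.4-1 and footnote f | Appendix 4 |
|---|---|---|
| Population | Peri-menopausal (not defined) | Post-menopausal |
| FSH threshold | None | Above 40 mIU/mL |
| Age | None | Over 45; FSH also required if under 55 |
| Amenorrhea | None | 12 months, no other cause |
| Hormonal washout | Not mentioned | FSH above 40 mIU/mL at any time in it suffices |
| Cross-reference to the other | None | None |

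**Cases, for women not permanently sterile**

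1. Aged 46 to 54, 12 months of amenorrhea, no FSH test. Appendix 4: WOCBP. The table entries say nothing that changes this. No conflict.
2. The same woman with FSH above 40 mIU/mL. Not WOCBP on either text. No conflict.
3. Aged 46 to 54, less than 12 months of amenorrhea, FSH above 40 mIU/mL, not in a hormonal washout. Appendix 4: WOCBP, because the amenorrhea condition is not met. Table entries read literally: FSH may exclude childbearing potential. **Conflict.**
4. Aged 55 or over, 12 months of amenorrhea. Appendix 4: not WOCBP, and FSH is not needed. No conflict.
5. Aged 55 or over, less than 12 months of amenorrhea, called peri-menopausal, raised FSH, not in a washout. Same **conflict** as case 3.
6. Aged 45 or younger, not in a washout. Appendix 4: WOCBP. The table entries have no age limit, so they **conflict** if she is called peri-menopausal and has a raised FSH.
7. In a hormonal washout, FSH above 40 mIU/mL. Appendix 4 itself allows her to be considered postmenopausal, so it does not oppose the table entries. The list of washout intervals has no lead-in in the text available for this review, possibly because text was lost, so its exact scope is uncertain.

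The disagreement is confined to cases 3, 5 and 6: called peri-menopausal, raised FSH, amenorrhea or age condition not met, and outside a washout.

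**Precedence.** Appendix 4 describes itself as general material and sends the reader to Section 6.1 for this study's contraception requirements. Section 6.1 points back to Appendix 4 for methods and supplies no definition. No text says whether the schedule footnote or the appendix governs.

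**The case against.** The strongest reply is that only one rule exists. The two table entries are test listings, and they carry no threshold because they define nothing. Appendix 4 is the definition, and FSH is its confirmatory test. On that view a careful investigator reads the listing through the appendix and no woman is misclassified. Section 6.1 adds safeguards: evidence of non-childbearing status must be in source documents, and the investigator must review medical and menstrual history.

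Much of this stands. It narrows the problem to a small group and makes a wrong classification less likely. It does not remove the mismatch. The entries go beyond listing a test: they say what it may be used to conclude, and for whom, and Appendix 4 does not support that conclusion for that population. The source-document rule does not help either, because it does not say which evidence is enough.

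A reader might also infer that calling FSH optional in the tables contradicts its being mandatory under 55 in Appendix 4. The documents do not support this. A test can be optional for the study and still be necessary for a woman under 55 who is to be classed as postmenopausal. If it is not done, she stays WOCBP, and neither table says otherwise. Nor does Appendix 4 always demand amenorrhea together with FSH, since its washout sentence lets FSH suffice.

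**Conclusion.** The inconsistency is real but narrow. Footnote f and Table 9.5.4-1 allow a conclusion about peri-menopausal women that Appendix 4 does not allow, and the passages give different status to the group in cases 3, 5 and 6 only. This rests on reading the two entries literally and on Appendix 4 being the only WOCBP definition in the document.

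The number of women affected cannot be stated. A reader might multiply the 250 planned treated participants by assumed shares of women and of peri-menopausal age. The documents give no sex or age distribution, no frequency of FSH testing and no definition of peri-menopausal. Such a count would also take in women for whom there is no conflict, such as case 1.

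No endpoint, analysis set, sample size or confidence interval is touched. The point merits correction because the status governs protection against fetal exposure and no scheduled pregnancy test follows Day 1.

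**What to change.** Reconcile Table 2-1 footnote f, the FSH entry in Table 9.5.4-1 and Appendix 4, including its washout sentence, so that one definition sets childbearing status. The reconciled text should settle who needs FSH, whether FSH alone can be enough and in what circumstances, and which threshold applies. Both table entries should then cite that definition instead of stating a use of their own. Which rule applies is for the sponsor's safety physicians to decide; this review takes no position on it.

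The cost is a wording change in two tables and one appendix. FSH is already available as a screening test, so the rewording itself adds no new type of test and no visit.
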